10.1.2 STUDY DISCONTINUATION AND CLOSURE

The study may be modified or discontinued at any time by the NINDS, the FDA, or other government agencies as part of their duties to ensure that research subjects are protected.

10.1.3 CONFIDENTIALITY AND PRIVACY

The subject's identity will be kept as confidential as possible as required by law. Upon enrollment,

WebDCU[™] assigns a unique subject ID to each subject. The link between the subject ID and the subject's name will be confidentially maintained at the enrolling sites. In compliance with Health Information Portability and Accountability Act (HIPAA), collection, storage, display, and transfer of study subject personal identifiers in the WebDCU[™] are carefully controlled. Prior to creating the Public Use Dataset any personal identifiers, such as date of enrollment, will be de-identified.

10.1.4 Key Roles and Study Governance

The HOBIT trial will be conducted in the SIREN network funded by the National Institutes of Neurological Disorders and Stroke (NINDS) and the National Heart, Lung, and Blood Institute (NHLBI). The Clinical Coordinating Center (CCC) for the HOBIT trial will be the SIREN CCC at the University of Michigan and the Data Coordinating Center (DCC) will be the SIREN DCC at the Medical University of South Carolina working with the Analytical Center (AC) at the University of Kansas for the adaptive design component. The Scientific Coordinating Center (SCC) will be at the University of Minnesota/Hennepin County Medical Center (HCMC).

Clinical Coordinating Center (CCC). The CCC is responsible for coordinating the Network and HOBIT enrolling site leadership and for overall organization, administration, and communication. These responsibilities include site management (regulatory management, enrollment performance, data monitoring, etc.), trial management (coordination of trial recruitment, publications, clinical translation), and management of study operations (protection of human subjects, outcomes assessment, training and education, etc.). The SIREN CCC has a Financial Specialist who will provide management and reconciliation of the HOBIT financial activities within the SIREN CCC, including review and processing of invoices for HOBIT funded activity and enrollment at the clinical sites.

Data Coordinating Center (DCC). The main responsibilities of the DCC are to provide the database, data management, and statistical support for the HOBIT trial. The DCC will be responsible for data processing and management of data obtained at all study sites and generation and distribution of progress reports as well as reports to the Data and Safety Management Board (DSMB). The DCC will also implement the adaptive design procedure provided by the Analytic Center for interim analyses and provide statistical support throughout the trial.

Analytic Center (AC). The AC is responsible for the Bayesian adaptive portion of the project. The AC will write and validate the computer code of the adaptive design procedure and perform final statistical analysis. He will be responsible for providing initial adaptive design study interpretations and reviewing and verifying all conclusions drawn from these analyses.

Scientific Coordinating Center (SCC). The SCC consists of the contact PI, the clinical project coordinator (CPC), the internal quality reviewer (IQR), and the HOBIT trial financial manager (FM). The PI provides overall leadership to the entire HOBIT trial to ensure a successful implementation. He is specifically responsible for monitoring the conduct and progress of the clinical investigations as well as reviewing and evaluating the information relevant to the safety of hyperbaric oxygen (HBO) administration. The

CPC assists the PI in day-to-day implementation in various trial activities. The IQR will be responsible for reviewing adverse events (AE) prior to being forwarded to the independent medical safety monitor (IMSM). The IQR will also assist the PI, the CPC, CCC and DCC in monitoring protocol compliance. The FM, together with the PI, is responsible for subcontracts to the CCC, the DCC, and the AC.

Executive Committee (EC). The EC consists of the leadership of the SCC, the CCC, the DCC and the AC and an NINDS-appointed liaison. The EC is a working group responsible for the development and amendment of the study documents (e.g., protocol, case report forms and manual of procedures), collection, review, and oversight of dissemination of SAEs (occurrences and other important events pertinent to the study), and communication among all components of the study participants (e.g., CCC, DCC, clinical sites, and the NINDS).

External Steering Committee (ESC). The ESC membership is composed of nationally recognized leaders in the fields of traumatic brain injury (TBI), critical care hyperbaric medicine, and clinical trials. The ESC serves in an advisory capacity to the study scientific leadership.

Independent Medical Safety Monitor (IMSM). The IMSM is a neurointensivist experienced in severe TBI management. The IMSM is not affiliated with any of the institutions participating in the HOBIT trial. The IMSM responsibilities are to review all SAEs and determine whether they are serious, possibly related to HBO administration, and unexpected. If all three criteria are met, expedited reporting the the FDA and cIRB will be initiated. The IMSM will have a backup neurointensivist in the unlikely event she is unable to review the SAEs in a timely manner.

Data and Safety Monitoring Board (DSMB). The DSMB is appointed by the NINDS director and managed by the NINDS clinical trials group. Its overarching responsibility is the oversight of safety of the trial participants. They review reports on SAEs, request additional data/information if necessary, and must be cognizant of external new information regarding the safety of HBO treatment. Upon review of the periodic data, they advise the NINDS regarding continuation of the trial.

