2.3.3 Assessment of Potential Risks and Benefits

Safety Record for Hyperoxia Treatment. An exemplary safety record for HBO treatment has been demonstrated over the course of four clinical trials at the Hennepin County Medical Center (Gossett 2010, Rockswold 1992, Rockswold 2001, Rockswold 2010, Rockswold 2013). There were 1,984 HBO treatments delivered to 167 subjects with no permanent complications related to the HBO treatment and no subject emergently evacuated from the chamber. In August 2015, the Food and Drug Administration (FDA) gave the HOBIT Trial a "Study May Proceed" notification. All SAEs for our four clinical trials were presented for the FDA review. All of the HBO chambers at our enrolling sites have been granted an investigational device exemption (IDE) and certified for safety by the FDA. Overall, there are four essential factors in maintaining the safety of the severe TBI subject during HBO treatment. First is that the inclusion/exclusion criteria for the subject's respiratory status must meet the criteria outlined in the protocol. Second, it is essential that the same level of care provided in the ICU be continued throughout the subject's transport to and from the HBO chamber (Weaver

1999). Third, the HBO chamber and its environment must become an extension of the ICU. Expertise of appropriate personnel must be as readily available in the HBO environment as it is in the ICU. Unlike the ICUs where the subjects may be left unattended for brief periods of time, the subject is under the constant observation and supervision by several staff members during the HBO treatment. Fourth, the safe application of HBO requires an additional set of skills, knowledge base, and experience that are unique to hyperbaric medicine and essential to the subject and staff safety. A well trained staff of hyperbaric nurses and technicians working under the supervision of a qualified HBO physician, each of whom have a thorough knowledge of the procedures and physiology of HBO therapy, is required. All clinical sites participating in the HOBIT Trial have a team of trained personnel who are aware and fully capable of carrying out these critical procedures.

The subjects receiving NBH (100% FiO2 at 1 ATA) will remain in the ICU to receive their treatments. There would be no increased risk of AEs compared to controls (standard treatment) other than the potential of O2 toxicity.

30	3 OBJECTIVES AND ENDPOINTS							

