6 STUDY INTERVENTION

6.1 STUDY INTERVENTION(S) ADMINISTRATION

6.1.1 STUDY INTERVENTION DESCRIPTION

The study interventions will be hyperbaric oxygen with or without additional normobaric hyperoxia or normobaric hyperoxia alone (NBH), or routine care (no hyperoxia). Hyperbaric oxygen therapy consists of breathing 100% oxygen (hyperoxia) while under increased atmospheric pressure.

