6.1.2 DOSING AND ADMINISTRATION

HBO Treatments

If the subject meets inclusion criteria, has no exclusions and informed consent is obtained or is enrolled with exception from informed consent, they will be randomized to either one of six HBO treatment paradigms, one NBH treatment paradigm, or the control group. Oxygen toxicity unit (OTU) is a means of quantifying the amount of O2 exposure to the subject based on duration and pressure. Despite its name, OTU is not actually a measure of oxygen toxicity. For the purposes of this study, OTUs will be used as a measure of oxygen dose. The OTUs for the different treatment groups are listed in the table below.

Tre	atment	Oxygen toxicity Unit (OTU)
1.	1.5 ATA 60 minutes twice a day	130 x 2 = 260
2.	2.0 ATA 60 minutes twice a day	208 x 2 = 416
3.	NBH (100% O2 at 1.0 ATA) 4.5 hours twice a day	270 x 2 = 540
4.	2.5 ATA 60 minutes twice a day	296 x 2 = 592
5.	1.5 ATA 60 minutes with 3 hours of NBH twice a day	310 x 2 = 620
6.	2.0 ATA 60 minutes with 3 hours of NBH twice a day	388 x 2 = 776
7.	2.5 ATA 60 minutes with 3 hours of NBH twice a day	476 x 2 = 952
8.	Control (no hyperoxia treatment)	

For subjects receiving HBO treatment, bilateral myringotomies will be performed prior to the first treatment. For all randomized subjects, ICP will be monitored during HBO treatments and ICP will be recorded every 15 minutes. Brain tissue PO2is optional. Brain tissue PO2 values should be recorded every 15 minutes during HBO treatment HBO treatments will be delivered in both monoplace and multiplace chambers. Compression and decompression will occur at a standard 2 feet per minute. Total compression/decompression time for 2.5 ATA is 50 minutes, for 2.0 ATA is 33 minutes, and for 1.5 ATA is 16.5 minutes. Each treatment will be for 60 minutes at the specified pressure. NBH will consist of the subject breathing 100% O2 for 3 hours following HBO decompression which will be continued in the ICU. The NBH without HBO treatment arm will likewise be ventilated with 100% O2 for 4.5 hours at 1.0 ATA in the ICU. The second dive will be administered at least 8 hours following the first dive. Subsequent dives will be administered at 12 hour intervals (+/- 2 hours) for a maximum of 10 dives or until the subject is following commands or determined to be brain dead. The time intervals are defined as from the start of the one dive to the start of the next dive. The first dive of the study should be

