8.4.3.2 RELATIONSHIP TO STUDY INTERVENTION

Adverse reaction is different than an adverse event. Suspected adverse reaction means any adverse event for which there is a reasonable possibility that the study intervention caused the adverse event. For the purposes of IND safety reporting, 'reasonable possibility' means there is evidence to suggest a causal relationship between the study intervention and the adverse event. A suspected adverse reaction implies a lesser degree of certainty about causality than adverse reaction, which means any adverse event is definitely caused by the study intervention.

Per FDA guidance a suspected adverse reaction is one that is known to be strongly associated with the study intervention, or one that is very uncommon in study population, or one shown in aggregate analysis to occur more frequently in the treatment group. Generally anticipated adverse events are not suspected adverse reactions.

Because 'reasonable possibility' can be difficult to determine, this trial uses an algorithmic approach to describing relatedness.

Algorithm to Dete	Algorithm to Determine Relatedness of Adverse Event to Study Agent			
Not Related	The temporal relationship between treatment exposure and the adverse event is unreasonable or incompatible and/or adverse event is clearly due to extraneous causes (e.g., underlying disease, environment)			
Unlikely	Must have both of the following 2 conditions, but may have reasonable or only tenuous temporal relationship to intervention.			

	 Could readily have been produced by the subject's clinical state, or environmental or other interventions. Does not follow known pattern of response to intervention.
	Must have at least 2 of the following 3 conditions
Reasonable Possibility	 Has a reasonable temporal relationship to intervention. Could not readily have been produced by the subject's clinical state or environmental or other interventions. Follows a known pattern of response to intervention.
Definitely	Must have all 3 of the following conditions
. -	 Has a reasonable temporal relationship to intervention. Could not possibly have been produced by the subject's clinical state or have been due to environmental or other interventions. Follows a known pattern of response to intervention.

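### The written trigger for expedited SAE reporting is relatedness to HBO, which on its face leaves out the NBH-only arm and conflicts with the protocol's own study-intervention standard

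*Protocol*

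**What the plan says.** Section 10.1.4 (Key Roles and Study Governance) gives the independent medical safety monitor the task to "review all SAEs and determine whether they are serious, possibly related to HBO administration, and unexpected". It continues: "If all three criteria are met, expedited reporting" to the FDA and the central IRB is started. The three tests are cumulative.

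Section 6.1.1 lists the study interventions as "hyperbaric oxygen with or without additional normobaric hyperoxia or normobaric hyperoxia alone (NBH"), or routine care. It then defines the hyperbaric component: "Hyperbaric oxygen therapy consists of breathing 100% oxygen (hyperoxia) while under increased atmospheric pressure".

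The arm table in section 6.1.2 has one arm with no pressure component, "NBH (100% O2 at 1.0 ATA) 4.5 hours twice a day", and three arms in which NBH is added to HBO. For those three, "NBH will consist of the subject breathing 100% O2 for 3 hours following HBO decompression".

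On the NBH subjects, who stay in the ICU, section 2.3.3 says: "There would be no increased risk of AEs compared to controls (standard treatment) other than the potential of O2 toxicity".

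Section 8.4.3.2 sets the relatedness standard: "Suspected adverse reaction means any adverse event for which there is a reasonable possibility that the study intervention caused the adverse event". It explains the reasonable-possibility test expressly for IND safety reporting, as evidence of a causal link with the study intervention. Section 8.4.4 collects relatedness to the study intervention for reported events, and section 8.4.5 refers reporting detail to a separate safety monitoring plan.

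**The concern.** The monitor's second test names HBO, while the intervention under study is wider than HBO. A subject randomized to NBH alone is never pressurized. A serious, unexpected event that a site attributes to the study intervention in that arm would then satisfy section 8.4.3.2 but fail the written test in section 10.1.4. The two sections cannot both be followed for that arm.

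The monitor's decision has direct consequences: the data collection schedule in section 1.3 makes the MedWatch form depend on the monitor. What is at stake is whether the expedited route to the FDA and central IRB is open on the same terms in every active arm.

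The narrow wording recurs nearby. Section 10.1.4 ties the principal investigator's review of safety information to HBO administration, and ties the DSMB's duty to follow new external safety information to HBO treatment.

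**Working it through.** The protocol states no figure for this point, so the check is mainly textual, with simple counts for scale.

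**Step 1: is NBH a form of HBO in this protocol?**
- Section 6.1.1 makes increased atmospheric pressure part of the definition of HBO. The NBH-only arm is at 1.0 ATA (section 6.1.2).
- Sections 1.1 and 6.1.2 randomize to six HBO groups, one NBH group and control, so NBH is counted apart from HBO.
- Section 2.3.3 keeps NBH subjects in the ICU for treatment.
- Section 8.5 speaks of non-HBOT groups in the plural, which fits control plus NBH.

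On the definitions, NBH is not HBO.

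**Step 2: apply the two standards to each type of active arm.**

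| Arm type | Number of arms | Section 8.4.3.2 (study intervention) | Section 10.1.4 (HBO administration) |
|---|---|---|---|
| HBO only | 3 | can be met | can be met |
| HBO + NBH | 3 | can be met | can be met: NBH directly follows HBO and the threshold is only possible relatedness |
| NBH only | 1 | can be met | cannot be met as written |

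The conflict is certain in one arm.

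**Step 3: scale.** Burn-in allocation (section 6.3): 11 control, 6 in each of six active arms, and 9 in 2.5 ATA+NBH.
- Total: 11 + 6×6 + 9 = 56, which agrees with the stated 56.
- NBH only: 6/56 = 10.7%.
- Any NBH: 6 + 6 + 6 + 9 = 27, and 27/56 = 48.2%. This second figure counts who receives NBH. It does not count who is excluded by the wording.
- After burn-in, allocation is adaptive, so the NBH-only share can rise or fall.

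**Step 4: is the excluded exposure trivial?** By the section 6.1.2 table, the daily oxygen dose is 540 OTU in the NBH-only arm, against 260 at 1.5 ATA and 416 at 2.0 ATA. Two arms with a lower OTU dose are inside the trigger while the NBH-only arm is outside it. Section 6.1.2 says that the OTU is used as a measure of dose and does not measure toxicity. The comparison therefore shows only that the NBH-only arm is not a low-exposure arm. It does not estimate any number of missed reports.

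**The case against.** **The operative standard may be the wider one.** Section 8.4.3.2 is the provision that speaks to IND safety reporting, and it covers NBH. Section 10.1.4 is a summary of roles, and the working procedure is in a safety monitoring plan that is not at hand. This stands as far as it goes: it cannot be said that any report was or would be missed. It does not remove the contradiction, because section 10.1.4 is where the protocol states the three tests and their consequence.

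**HBO may be shorthand for all hyperoxia.** Section 3 calls the aim the most effective hyperbaric oxygen paradigm although NBH is a candidate arm. Section 9.1 equates hyperbaric oxygen with hyperoxia, and section 7.2 glosses stopping the intervention as no HBO treatments. A monitor might well read the phrase broadly. That is plausible, but section 6.1.1 points the other way, and a reporting trigger should not depend on which reading is chosen.

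**Stronger readings that a reader might infer, and that the documents do not support:**
- *That NBH events in all four NBH-containing arms are shut out.* In the three combination arms NBH follows decompression in the same treatment session, so an event can readily be judged possibly related to HBO.
- *That NBH's share of the OTU dose in those arms measures the problem.* It says nothing about which SAEs pass the test.
- *That the comparison of SAEs across arms is biased.* Section 9.4 summarizes all AEs and SAEs by treatment group and compares cumulative incidences of SAEs. Expedited reports do not feed that analysis. The monitor reviews all SAEs, and the DSMB reviews SAE reports.
- *That ordinary oxygen-toxicity events would be expedited in HBO arms but not under NBH.* The event must also be unexpected. Oxygen toxicity is the acknowledged NBH risk, and section 9.4 lists pulmonary dysfunction and pneumonia with expected dose relations. Many such events could fail that test in any arm.

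**Conclusion.** The point holds as an internal contradiction in the protocol. As written, the trigger in section 10.1.4 excludes the NBH-only arm and is narrower than the study-intervention standard in sections 6.1.1, 8.4.3.2 and 8.4.4. Its certain reach is one of seven active arms, 6 of 56 burn-in subjects (10.7%), and only the expedited route is affected. No missed report is shown.

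The conclusion assumes that HBO in section 10.1.4 carries the meaning given in section 6.1.1. If the safety monitoring plan already uses the study intervention as its reference, the practical effect may be nil, but the protocol text would still need correcting. It is worth correcting because it concerns safety oversight and costs almost nothing.

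**What to change.** - In section 10.1.4, change the monitor's second test to *possibly related to the study intervention (HBO or NBH)*, so that it agrees with sections 6.1.1, 8.4.3.2 and 8.4.4.
- In the same section, align the HBO-only wording of the principal investigator's and the DSMB's safety duties.
- Check the safety monitoring plan and change it if it repeats the HBO-only phrase.
- Confirm that SAEs already adjudicated in the NBH-only arm were judged against the study intervention. This is a confirmation and does not presume that any were misjudged.

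The cost is a short amendment, a brief check of one arm's SAEs, and possibly a few more expedited reports. Design, sample size and analysis are unaffected.

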10.1.5 SAFETY OVERSIGHT

Data Safety Monitoring Board. The DCC will generate safety and other reports as requested by the DSMB.

10.1.6 QUALITY ASSURANCE AND QUALITY CONTROL

See monitoring plan for details

Clinical site monitoring is conducted to ensure that the rights and well-being of human subjects are protected, that the reported trial data are accurate, complete, and verifiable, and that the conduct of the trial is in compliance with the currently approved protocol/amendment(s), with GCP, with applicable FDA regulations (21 CFR 312), and with the FDA's "Guidance for Industry Oversight of Clinical Investigations — A Risk-Based Approach to Monitoring." Monitoring for this study will be performed by the DCC/CCC centrally, on site, and remotely. Per the study's monitoring plan, monitoring will include a combination of on-site monitoring (to verify data entered into the WebDCU[™] database against source documents and query inaccuracies between the source documents and WebDCU[™] database), remote

monitoring (source document verification, including verification of written consent, may be performed remotely by reviewing source documents that have been uploaded into WebDCU[™] or via remote access to electronic medical records), and central monitoring (using web-based data validation rules, data manager review of entered data, statistical analysis, and on-going review of site metrics). Further details of clinical site monitoring are documented in the study's Monitoring Plan.

The EC, on a regular basis, will review a summary of the data entered in the HOBIT WebDCU[™] database by the participating clinical sites to identify deficiencies in data collection and/or entry. This summary will be the result of the ongoing review by the DCC Data Manager (DM) and IMSM of data entered by all participating clinical sites.

10.1.7 STUDY RECORDS RETENTION

Refer to the manual of procedures for additional details on retention of study records.

10.1.8 PROTOCOL DEVIATIONS

At regular intervals, the EC will review the material and discuss, among other items, any concerns regarding the principles and intensity of the overall care and aggregations of protocol violations/deviations at particular sites. The EC may recommend that individual sites be contacted to discuss the issues identified at those sites and potential remedial measures. As a result of these reviews, the EC may make recommendations for protocol changes if serious safety concerns arise or there is an overarching issue with implementation of the protocol.

